22 to 35 days of age (male and female)	9.5 to 11.0 5.88 to 6.86	8.0 to < 9.5 4.94 to < 5.88	6.7 to < 8.0 4.15 to < 4.94	< 6.7 < 4.15
8 to ≤ 21 days of age (male and female)	11.0 to 13.0 6.81 to 8.10	9.0 to < 11.0 5.57 to < 6.81	8.0 to < 9.0 4.96 to < 5.57	< 8.0 < 4.96
≤ 7 days of age (male and female)	13.0 to 14.0 8.05 to 8.72	10.0 to < 13.0 6.19 to < 8.05	9.0 to < 10.0 5.59 to < 6.19	< 9.0 < 5.59
INR, High (not on anticoagulation therapy)	1.1 to < 1.5 x ULN	1.5 to < 2.0 x ULN	2.0 to < 3.0 x ULN	≥ 3.0 x ULN
Methemoglobin (%) hemoglobin)	5.0 to < 10.0%	10.0 to < 15.0%	15.0 to < 20.0%	≥ 20.0%

PARAMETER	GRADE 1 MILD	GRADE 2 MODERATE	GRADE 3 SEVERE	GRADE 4 POTENTIALLY LIFE-THREATENING
PTT, High (not on anticoagulation therapy)	1.1 to < 1.66 x ULN	1.66 to < 2.33 x ULN	2.33 to < 3.00 x ULN	≥ 3.00 x ULN
Platelets, Decreased (cells/mm ³ ; cells/L)	100,000 to < 124,999 100.000×10^9 to < 124.999×10^9	50,000 to < 100,000 50.000×10^9 to < 100.000×10^9	25,000 to < 50,000 25.000×10^9 to < 50.000×10^9	< 25,000 < 25.000×10^9
PT, High (not on anticoagulation therapy)	1.1 to < 1.25 x ULN	1.25 to < 1.50 x ULN	1.50 to < 3.00 x ULN	≥ 3.00 x ULN
WBC, Decreased (cells/mm ³ ; cells/L) > 7 days of age	2,000 to 2,499 2.000×10^9 to 2.499×10^9	1,500 to 1,999 1.500×10^9 to 1.999×10^9	1,000 to 1,499 1.000×10^9 to 1.499×10^9	< 1,000 < 1.000×10^9
≤ 7 days of age	5,500 to 6,999 5.500×10^9 to 6.999×10^9	4,000 to 5,499 4.000×10^9 to 5.499×10^9	2,500 to 3,999 2.500×10^9 to 3.999×10^9	< 2,500 < 2.500×10^9
URINALYSIS				
Glycosuria (random collection tested by dipstick)	Trace to 1+ or ≤ 250 mg	2+ or > 250 to ≤ 500 mg	> 2+ or > 500 mg	NA
Hematuria (not to be reported based on dipstick findings or on blood believed to be of menstrual origin)	6 to < 10 RBCs per high power field	≥ 10 RBCs per high power field	Gross, with or without clots OR With RBC casts OR Intervention indicated	Life-threatening consequences
Proteinuria (random collection tested by dipstick)	1+	2+	3+ or higher	NA

1. Blood pressure norms for children < 18 years of age can be found in: Expert Panel on Integrated Guidelines for Cardiovascular Health and Risk Reduction in Children and Adolescents [Pediatrics, 2011];128;S213; originally published online November 14, 2011; DOI: 10.1542/peds.2009-2107C.
2. As per Bazett's formula.
3. For pruritus associated with injections or infusions, see the *Site Reactions to Injections and Infusions* section (page 23).
4. Definition: A disorder characterized by fat loss in the face, extremities, and buttocks.
5. Definition: A disorder characterized by abnormal fat accumulation on the back of the neck, breasts, and abdomen.
6. BMD t and z scores can be found in: [Kanis, 2007]JA on behalf of the World Health Organization Scientific Group (2007). Assessment of osteoporosis at the primary health-care level. Technical Report. World Health Organization

Collaborating Centre for Metabolic Bone Diseases, University of Sheffield, UK. 2007: Printed by the University of Sheffield.

7. Definition: A delivery of a live-born neonate occurring at ≥ 20 to < 37 weeks gestational age.
8. Definition: A clinically recognized pregnancy occurring at < 20 weeks gestational age.
9. Definition: A disorder characterized by nausea, headache, tachycardia, hypotension, rash, and/or shortness of breath.
10. For pain associated with injections or infusions, see the *Site Reactions to Injections and Infusions* section (page 23).
11. Definition: A disorder characterized by fever, arthralgia, myalgia, skin eruptions, lymphadenopathy, marked discomfort, and/or dyspnea.
12. WHO reference tables may be accessed by clicking the desired age range or by accessing the following URLs:
http://www.who.int/growthref/who2007_bmi_for_age/en/ for participants > 5 to 19 years of age and
http://www.who.int/childgrowth/standards/chart_catalogue/en/ for those ≤ 5 years of age.
13. Injection Site Erythema or Redness should be evaluated and graded using the greatest single diameter or measured surface area.
14. Direct bilirubin > 1.5 mg/dL in a participant < 28 days of age should be graded as grade 2, if $< 10\%$ of the total bilirubin.
15. Use the applicable formula (i.e., Cockcroft-Gault in mL/min or Schwartz in mL/min/1.73m²).
16. To convert a magnesium value from mg/dL to mmol/L, laboratories should multiply by 0.4114.
17. Male and female sex are defined as sex at birth.
18. The conversion factor used to convert g/dL to mmol/L is 0.6206 and is the most commonly used conversion factor. For grading hemoglobin results obtained by an analytic method with a conversion factor other than 0.6206, the result must be converted to g/dL using the appropriate conversion factor for the particular laboratory.

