Potassium, Low (mEq/L; mmol/L)	3.0 to < 3.4 3.0 to < 3.4	2.5 to < 3.0 2.5 to < 3.0	2.0 to < 2.5 2.0 to < 2.5	< 2.0 < 2.0
Sodium, High (mEq/L; mmol/L)	146 to < 150 146 to < 150	150 to < 154 150 to < 154	154 to < 160 154 to < 160	≥ 160 ≥ 160
Sodium, Low (mEq/L; mmol/L)	130 to < 135 130 to < 135	125 to < 130 125 to < 135	121 to < 125 121 to < 125	≤ 120 ≤ 120
Uric Acid, High (mg/dL; mmol/L)	7.5 to < 10.0 0.45 to < 0.59	10.0 to < 12.0 0.59 to < 0.71	12.0 to < 15.0 0.71 to < 0.89	≥ 15.0 ≥ 0.89
HEMATOLOGY				
Absolute CD4+ Count, Low (cell/mm ³ ; cells/L)	300 to < 400 300 to < 400	200 to < 300 200 to < 300	100 to < 200 100 to < 200	< 100 < 100
> 5 years of age (not HIV infected)				
Absolute Lymphocyte Count, Low (cell/mm ³ ; cells/L)	600 to < 650 0.600 x 10 ⁹ to < 0.650 x 10 ⁹	500 to < 600 0.500 x 10 ⁹ to < 0.600 x 10 ⁹	350 to < 500 0.350 x 10 ⁹ to < 0.500 x 10 ⁹	< 350 < 0.350 x 10 ⁹
> 5 years of age (not HIV infected)				

PARAMETER	GRADE 1 MILD	GRADE 2 MODERATE	GRADE 3 SEVERE	GRADE 4 POTENTIALLY LIFE-THREATENING
Absolute Neutrophil Count (ANC), Low (cells/mm ³ ; cells/L) ≥ 7 days of age	800 to 1,000 0.800×10^9 to 1.000×10^9	600 to 799 0.600×10^9 to 0.799×10^9	400 to 599 0.400×10^9 to 0.599×10^9	< 400 $< 0.400 \times 10^9$
2 to 7 days of age	1,250 to 1,500 1.250×10^9 to 1.500×10^9	1,000 to 1,249 1.000×10^9 to 1.249×10^9	750 to 999 0.750×10^9 to 0.999×10^9	< 750 $< 0.750 \times 10^9$
≤ 1 day of age	4,000 to 5,000 4.000×10^9 to 5.000×10^9	3,000 to 3,999 3.000×10^9 to 3.999×10^9	1,500 to 2,999 1.500×10^9 to 2.999×10^9	< 1,500 $< 1.500 \times 10^9$
Fibrinogen, Decreased (mg/dL; g/L)	100 to < 200 1.00 to < 2.00 OR 0.75 to < 1.00 x LLN	75 to < 100 0.75 to < 1.00 OR 0.50 to < 0.75 x LLN	50 to < 75 0.50 to < 0.75 OR 0.25 to < 0.50 x LLN	< 50 < 0.50 OR $< 0.25 \times LLN$ OR Associated with gross bleeding
Hemoglobin ¹⁷ , Low (g/dL; mmol/L) ¹⁸ ≥ 13 years of age (male only)	10.0 to 10.9 6.19 to 6.76	9.0 to < 10.0 5.57 to < 6.19	7.0 to < 9.0 4.34 to < 5.57	< 7.0 < 4.34
≥ 13 years of age (female only)	9.5 to 10.4 5.88 to 6.48	8.5 to < 9.5 5.25 to < 5.88	6.5 to < 8.5 4.03 to < 5.25	< 6.5 < 4.03
57 days of age to < 13 years of age (male and female)	9.5 to 10.4 5.88 to 6.48	8.5 to < 9.5 5.25 to < 5.88	6.5 to < 8.5 4.03 to < 5.25	< 6.5 < 4.03
36 to 56 days of age (male and female)	8.5 to 9.6 5.26 to 5.99	7.0 to < 8.5 4.32 to < 5.26	6.0 to < 7.0 3.72 to < 4.32	< 6.0 < 3.72

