| Part 1 
 
To compare the single dose PK of DTG conventional 10 mg tablets (5 tablets) administered direct to mouth as compared to a conventional 50 mg tablet (reference) administered direct to mouth.
 
                                                                                             | Part 1 
 
Plasma DTG tlag, tmax, t½, λz, %AUCex, AUC0-24, CL/F and Vz/F, Ct, and C24.
 
Safety and tolerability parameters as assessed by change from baseline in number of subjects with AEs and DAIDS toxicity grading for HIV-infected patients of clinical laboratory tests as described in Appendix
 
 |

| Objectives                                                                                                                                                                                                                                                                                                                                                                                                                                                                                                                                                                                                                                                                        | Endpoints                                                                                                                                                                                                                                                                                                                                                                                                    |

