**NOTES :**

1. Conditional display, it will only be produced when an event has occurred.
2. Displays contain only subjects with DAIDS toxicities for HIV-infected patients of Grade 2 or higher
3. Displays contain only subjects with abnormal findings
4. Displays contain only subjects with values of potential clinical importance
  - T = Table, F = Figure, L = Listing, Y = Yes display generated.
  - Summary = Represents TFL related to any summaries (i.e. descriptive statistics) of the observed raw data.
  - Individual = Represents TFL related to any displays of individual subject observed raw data.

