| 14                             | All Subjects | AE9CP                         | Listing of Study Drug Related Adverse Events                         |                   | SAC[1]                 |
| 15                             | All Subjects | SAFE_L2                       | Listing of Serious Adverse Events                                    |                   | SAC[1]                 |
| 16                             | All Subjects | AE9CP                         | Listing of Adverse Events Leading to Withdrawal from Study Drug      |                   | SAC[1]                 |
| 17                             | All Subjects | SAFE_L3                       | Listing of Liver Adverse Events                                      |                   | SAC[1]                 |

| ICH : Listings            |              |                               |                                                                                          |                   |                        |
|---------------------------|--------------|-------------------------------|------------------------------------------------------------------------------------------|-------------------|------------------------|
| No.                       | Population   | IDSL / TST ID / Example Shell | Title                                                                                    | Programming Notes | Deliverable [Priority] |
| Laboratory Values  |              |                               |                                                                                          |                   |                        |
| 18                        | All Subjects | LB6                           | Listing of Clinical Chemistry Toxicities of Grade 2 or Higher                            |                   | SAC [1]                |
| 19                        | All Subjects | LB6                           | Listing of All Clinical Chemistry Data for Subjects with Toxicities of Grade 2 or Higher |                   | SAC [1]                |
| 20                        | All Subjects | LB6                           | Listing of Haematology Toxicities of Grade 2 or Higher                                   |                   | SAC [1]                |
| 21                        | All Subjects | LB6                           | Listing of All Haematology Data for Subjects with Toxicities of Grade 2 or Higher        |                   | SAC [1]                |

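### The low-sodium Grade 2 cell in Protocol Appendix 6 contradicts itself (125 to <130 mEq/L but 125 to <135 mmol/L), so on the mmol/L line values from 130 to <135 carry two grades

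*Protocol*

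**What the plan says.** The grading table is in Protocol Section 12.6 (Appendix 6). The row in question begins "Sodium, Low (mEq/L; mmol/L", so each grade cell holds two ranges, mEq/L first and mmol/L second. Grade 1 reads "130 to < 135 130 to < 135", Grade 2 reads "125 to < 130 125 to < 135" and Grade 3 reads "121 to < 125 121 to < 125". Grade 4 is 120 or below on both lines.

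Sodium is one of the required clinical chemistry tests (Protocol Section 9.3.4, Table 5). SAP Section 2.2 describes the laboratory part of the secondary safety endpoint as "DAIDS toxicity grading for HIV-infected patients of clinical laboratory tests as described in Appendix" 6 of the protocol, so the SAP grades from this table. SAP Section 2.1 lowers the threshold for the toxicity listings from Grade 3 to Grade 2. Note 2 to SAP Table 5 (Section 8.1) applies that threshold: "Displays contain only subjects with DAIDS toxicities for HIV-infected patients of Grade 2 or higher". In SAP Section 10.10.8, Listing 18 is titled "Listing of Clinical Chemistry Toxicities of Grade 2 or Higher", and Listing 19 gives all chemistry data for the same subjects.

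**The concern.** The unit label cannot explain two different Grade 2 ranges. Sodium is monovalent, so 1 mEq/L equals 1 mmol/L and the two lines should be identical. With an upper limit of 135 on the mmol/L line, Grade 2 contains the whole of Grade 1.

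The conflict falls exactly at the SAP's listing threshold. A value of 132, for example, is Grade 1 in mEq/L and stays out of the listings. In mmol/L the same value also meets Grade 2, and it can bring the subject's full chemistry record into Listing 19. A Grade 3 threshold would have made the discrepancy harmless to the listings. At Grade 2, the content of two safety listings depends on which line the programmer reads and how a double match is handled.

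**Working it through.** No sample size or test is involved. The check treats each printed range as an interval that includes its lower limit and excludes its upper limit, looks for overlap between grades on each unit line, and then compares the cell with similar rows.

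**1. The low-sodium row as printed (Protocol Appendix 6)**

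| Grade | mEq/L | mmol/L | Lines agree? |
|---|---|---|---|
| 1 | 130 to <135 | 130 to <135 | yes |
| 2 | 125 to <130 | 125 to <135 | **no** |
| 3 | 121 to <125 | 121 to <125 | yes |
| 4 | 120 or below | 120 or below | yes |

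**2. Overlap of Grades 1 and 2.** The overlap runs from the larger lower limit to the smaller upper limit.

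- mEq/L: from max(130, 125) = 130 to min(135, 130) = 130. It is empty.
- mmol/L: from max(130, 125) = 130 to min(135, 135) = 135. It is 130 to <135, the whole of Grade 1.

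**3. Whole-number values graded on each line**

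| Sodium | Grade, mEq/L line | Grade(s), mmol/L line |
|---|---|---|
| 121 to 124 | 3 | 3 |
| 125 to 129 | 2 | 2 |
| 130, 131, 132, 133, 134 | 1 | 1 and 2 |
| 135 | none | none |

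Only 130 to 134 are ambiguous. The discrepancy can add a subject to the listings but cannot remove one, because 125 to 129 is Grade 2 on either line.

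**4. Which entry is out of line.** Five rows of Appendix 6 carry the mEq/L; mmol/L label for a monovalent ion: bicarbonate low, potassium high, potassium low, sodium high and sodium low. They have 5 × 4 = 20 grade cells, and 19 of them give the same figures in both units. High-sodium Grade 2, for instance, reads "150 to < 154 150 to < 154". The low-sodium Grade 2 cell is the one exception. Magnesium, a divalent ion, is halved in every cell (1.2 to <1.4 against 0.60 to <0.70 at Grade 1), so the table does convert where conversion is due. The mEq/L entry fits its neighbours without gap or overlap. The mmol/L entry does not.

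**5. Is there a rule that settles it?** Neither document says what to do when a value meets two grades, and neither fixes the reporting unit for sodium. SAP Section 10.4.3, where safety derivations are set out, covers ECG parameters and adverse events of special interest but not laboratory grading.

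**6. With the mmol/L entry set to 125 to <130.** The overlap becomes max(130, 125) = 130 to min(135, 130) = 130, which is empty. Values of 130 to 134 are then Grade 1 only and fall below the listing threshold.

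**The case against.** The strongest reply is that this is a clerical slip in a reproduced standard table, with almost no consequence. Much of that stands.

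- A reader might infer that the printed rule moves every Grade 1 low sodium into Grade 2. It does not. Grade 1 is still printed as 130 to <135 mmol/L, so such values meet both grades. Misgrading needs two further conditions, that the mmol/L line is programmed and that the higher matching grade is taken. Neither is documented.
- A reader might also infer that the row offers only a wrong range. It does not, because the mEq/L line in the same cell is sound.
- Nothing supports assuming that results will arrive in mmol/L. Outside Appendix 6 the protocol quotes creatinine (Section 3.3.1) and haptoglobin (Section 12.7.1) in mg/dL. That leaves the sodium unit open.
- The link to the secondary safety endpoint can suggest more than it delivers. SAP Tables 2.5 and 2.6 summarise change from baseline and Table 2.7 dipstick results, so no planned table counts laboratory grades. No formal safety analysis is planned either.
- No safety action turns on this cell. The laboratory alerts in Protocol Section 3.3.1 concern Grades 3 and 4, where the sodium entries agree. Appendix 7 has no sodium rule.

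What remains is that the contradiction is on the page, no rule resolves it, and it sits on a threshold that the SAP uses. For chemistry, Listings 18 and 19 are the only planned displays defined by toxicity grade. A single digit carries the point, so it is worth confirming on the original page, although the neighbouring cells are consistent.

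**Conclusion.** The point holds as an internal contradiction in one cell with a small, conditional effect on reporting. On the mmol/L line, all values from 130 to <135 are graded twice. If that line is programmed and the higher grade taken, mild values would wrongly appear in Listing 18, and the subject's full chemistry data would follow in Listing 19. If the mEq/L line is used, or the lower grade is taken, nothing changes.

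The documents do not support any wider effect. PK results, summary tables, Grade 3/4 alerts and stopping rules are untouched. Planned enrolment is about 14 + 24 = 38 healthy adults. How many will have a sodium value between 130 and <135 is not given. It is probably few and may be none. The conclusion assumes only that the two units are numerically equal for sodium and that the SAP grades from Appendix 6 as printed.

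**What to change.** Reconcile the two unit lines before laboratory grading is programmed, so that the mmol/L entry for low-sodium Grade 2 matches the non-overlapping mEq/L entry (125 to <130). This can be done in Protocol Appendix 6. If the protocol is not otherwise being amended, one sentence in SAP Section 10.4.3 can record the correction and say that sodium is graded from it. The cost is one table entry or one SAP line. No data collection, analysis or clinical procedure changes.

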12.7. Appendix 7: Toxicity Management

12.7.1. ANEMIA

Grade 1 (mild) hemoglobin decrease:

Any hemoglobin decrease meeting the definition of Grade 1 must be repeated with the following additional tests:

1. peripheral blood smear
2. indirect bilirubin (abnormal if increased >50% from baseline)
3. haptoglobin (abnormal if ≤ 25 mg/dL)
4. reticulocyte count (abnormal if $\geq 4\%$)

If the additional tests are within the normal range, subjects may continue study medication. If one or more of the additional tests is abnormal or suggestive of hemolytic anemia as specified above, subjects will permanently discontinue study medication and be withdrawn from the trial. Subjects should be followed up until resolution of anemia.

Grade 2 (moderate) hemoglobin decrease:

Any hemoglobin decrease meeting the definition of Grade 2 must be repeated with the following additional tests:

1. peripheral blood smear
2. indirect bilirubin (abnormal if increased >50% from baseline)
3. haptoglobin (abnormal if ≤ 25 mg/dL)
4. reticulocyte count (abnormal if $\geq 4\%$)

If the additional tests are within the normal range, subjects may continue study medication. If one or more of the additional tests is abnormal or suggestive of hemolytic anemia as specified above, subjects will permanently discontinue study medication and be withdrawn from the trial. Consultation with a Hematologist should be considered. Subjects should be followed up until resolution of anemia.

Grade 3 (severe) or Grade 4 (potentially life threatening) hemoglobin decrease:

Any hemoglobin decrease meeting the definition of Grade 3 or 4 must be repeated with the following additional tests:

1. peripheral blood smear
2. indirect bilirubin
3. haptoglobin
4. reticulocyte count

Subjects will permanently discontinue study medication and be withdrawn from the trial. Consultation with a Hematologist should be considered. Subjects should be followed up until resolution of anemia.

12.7.2. TOTAL BILIRUBIN ELEVATION

Grade 1 (mild) bilirubin elevation (1.1 - 1.5 times ULN) or Grade 2 (moderate - 1.6-2.5 times ULN):

Any bilirubin value above the upper limit of normal must be repeated and fractionated (direct and indirect bilirubin). Subjects may continue study medication. Subjects should be followed up until resolution (return to baseline) of elevation.

Grade 3 (severe – 2.6-5.0 times ULN) or 4 (life-threatening - >5.0 times ULN) bilirubin elevation:

Any bilirubin value above the upper limit of normal must be repeated and fractionated (direct and indirect bilirubin). Subjects will permanently discontinue study medication and be withdrawn from the trial. Subjects should be followed up until resolution (return to baseline) of bilirubin elevation.

12.7.3. AST AND ALT ELEVATION

See Section [12.2](#).

12.7.4. RASH

Grade 1 rash (Localized macular rash):

Subjects with Grade 1 rash should be evaluated by the Investigator immediately. A dermatologist may be consulted and a biopsy may be obtained if recommended by the dermatologist. The study drug should be permanently discontinued if the following signs or symptoms are noted at any time:

1. Temperature $>38.5^{\circ}\text{C}$
2. Lymphadenopathy
3. Pharyngitis
4. Any indication of internal organ involvement (hepatitis, nephritis)

In the absence of the above signs or symptoms, subjects with Grade 1 rash may continue the study drug at the discretion of the Investigator. The subject should be advised to contact the Investigator immediately if there is any worsening of the rash, if any systemic signs or symptoms worsen, or if mucosal ulceration develops. If the rash is considered to be most likely due to concomitant illness or non-study medication, standard management, including discontinuation of the likely causative agent, should be undertaken. If no other causative factor is found after clinical evaluation, the subject may be treated symptomatically until the rash resolves. Antihistamines, topical corticosteroids or antipruritic agents may be prescribed. The subject should remain on the study to be followed for safety and PK as outlined in Section [9.1](#) and Section [9.3](#).

Grade 2 rash (Diffuse macular, maculopapular, or morbilliform rash OR Target lesions):

Subjects with Grade 2 rash should be evaluated by the Investigator immediately. Digital photographs should be obtained. A dermatologist may be consulted and a biopsy may be obtained if recommended by the dermatologist. The study drug should be permanently discontinued if the following signs or symptoms are noted at any time:

1. Temperature >38.5°C
2. Lymphadenopathy
3. Pharyngitis
4. Any indication of internal organ involvement (hepatitis, nephritis)

In the absence of the above signs or symptoms, subjects with Grade 2 rash may continue the study drug at the discretion of the Investigator. It should be noted that oral mucosal **erosions** may be part of a Grade 2 rash. Any mucosal **ulceration** increases the severity of the rash to at least Grade 3. The subject should be advised to contact the Investigator immediately if there is any worsening of the rash, if any systemic signs or symptoms worsen, or if mucosal ulceration develops. If the rash is considered to be most likely due to concomitant illness or non-study medication, standard management, including discontinuation of the likely causative agent, should be undertaken. If no other causative factor is found after clinical evaluation, the subject may be treated symptomatically until the rash resolves. Antihistamines, topical corticosteroids or antipruritic agents may be prescribed. The subject should remain on the study to be followed for safety and PK as outlined in Section 9.1 and Section 9.3.

Grade 3 rash (Diffuse macular, maculopapular, or morbilliform rash with vesicles or limited number of bullae OR Superficial ulcerations of mucous membrane limited to one site):

Subjects with a Grade 3 rash will permanently discontinue the study medication. The subject should be evaluated in the physician's office immediately and should be seen in the physician's office or contacted by phone every 2 days until the rash resolves. A dermatologist should be consulted and digital photographs and a biopsy should be obtained. Antihistamines, topical corticosteroids or antipruritic agents may be prescribed at the discretion of the Investigator. The subject should be advised to contact the Investigator immediately if there is any worsening of the rash, if any systemic signs or symptoms appear, or if mucosal involvement develops. The subject should remain on the study to be followed for safety and PK as outlined in Section 9.1 and Section 9.3.

Grade 4 rash (Extensive or generalized bullous lesions OR Stevens-Johnson syndrome OR Ulceration of mucous membrane involving two or more distinct mucosal sites OR Toxic epidermal necrolysis (TEN)):

Subjects with a Grade 4 rash will permanently discontinue the study medication. A dermatologist should be consulted and digital photographs and a biopsy should be obtained. Sponsor and ViiV Medical Monitor should be notified of this serious adverse event within 24hr via phone or fax. The subject should be closely followed every day

until resolution of the reaction. The subject should remain on the study to be followed for safety and PK as outlined Section 9.1 and Section 9.3.

